4.4. Participant reported and other clinical outcomes

The proposed primary outcome for a future definitive outcome is change in alcohol use (grams of pure alcohol/week) between baseline and 180 days post-baseline. Alcohol use will be assessed using the Timeline Follow-Back technique³⁹ which is used to determine a patient's alcohol use over the 7 days immediately prior to their hospital admission (baseline) and at 28, 90 and 180 days post-baseline.

Alcohol use is challenging to measure objectively. Direct or indirect alcohol biomarkers are inaccurate or untested in patients with liver disease.⁴⁰ Self-monitoring, for example keeping a diary of alcohol use, is demanding for the patient, prone to missing data, and has a psychological impact through drawing attention to habitual use. The timeline follow-back method is a systematic tool to record alcohol use and avoids the reactivity of self-monitoring.⁴¹

Proposed participant reported secondary outcomes for a future definitive trial to be completed at baseline and 28, 90 and 180 days post-baseline are the:

- Severity of Alcohol Dependence Questionnaire (SADQ) is a validated 20 item questionnaire, which correlates with the degree of alcohol dependence⁴²
- EQ-5D-5L questionnaire to measure health-related Quality of life
- Warwick-Edinburgh Mental Wellbeing Scale (WEMWBS)⁴³ to measure mental wellbeing (including short form version (SWEMWBS))⁴⁴
- Health, social care and wider care services utilisation will be determined using a resource use questionnaire completed at baseline, day 90 and day 180
- Self-reported re-hospitalisation within 180 days post-baseline or, if unobtainable, determined using hospital records at participating sites
- Self-reported time to relapse to regular alcohol use (5 or more drinking days per week or 5 or more units in a single day).⁴⁵

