10. TRIAL SCHEDULE

[figure not shown]
This section describes the conduct of the trial in chronological order, detailing procedures for data collection at each of the time points. A summary flow chart is provided in Figure 1. A tabulated

summary of the trial schedule is given in

*TAU is delivered only once but can take place at any time during hospital admission and may occur before randomisation. **Table 1**. The trial involves four research visits (two face-to-face and two by telephone), each lasting approximately 60 minutes.

Figure 1: Trial Flowchart

*TAU is delivered only once but can take place at any time during hospital admission and may occur before randomisation.

Table 1: Tabulated summary of trial

		Pre- baseline	Baseline	Allocation		Post- allocation	
	TIMEPOINT		to		+28 days t1	+90 days t ₂	+180 days t₃
	ENROLMENT:						
	Eligibility screen	х	Х				
	Informed consent		х				
	Demographics		Х				
Medical History (Liver di	sease, Co-morbidities)		Х				
Historical Alcol	nol and Substance Use		Х				
Со	ncomitant medications		Х				
	/Allocation			Х			
	INTERVENTIONS:						
Intervention Group:	FIT		+				
	TAU				→		
Control Group:	ΤΑυ	+			→		
	ASSESSMENTS:						
	SADQ Score		Х		Х	х	х
	Current alcohol use [†]		Х		Х	Х	Х
WE	MWBS Questionnaire [‡]		Х		Х	Х	х
E	Q-5D-5L Questionnaire		Х		Х	Х	х
Health and Social Ca	are resource utilisation		Х			Х	х
Urine sample	for alcohol metabolites						х
5	SAFETY MONITORING:						
A	dverse event reporting		+				

[†]Self-reported alcohol use (units of alcohol) over a period of 7 days obtained using the timeline follow-back method (see section 10.1.1). At baseline, this covers the seven days prior to hospital admission. Post-allocation, this covers the seven days prior to the data collection timepoint.

t (including SWEMWBS)

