3 TRIAL DESIGN

3.1 GENERAL DESIGN

Multicentre randomised controlled pilot trial of FIT+TAU (intervention group) vs TAU alone (control group).

[figure not shown]

Figure 1: Flow of participants' progression through the MIRAGE pilot trial.

TAU comprises of one brief MI-based session given in hospital by the ALN. All participants should receive TAU. Due to local hospital practices, participants may have received TAU prior to being approached about this study, prior to giving informed consent, or prior to completing the baseline measures and being randomised. The FIT intervention comprises of one session given face-to-face to participants before discharge from hospital, a second session given, if possible, face-to-face to patients in an outpatient clinic or via telephone and then a further seven sessions delivered by telephone over a period of 6 months.

All participants will be scheduled for follow-up at 28 (± 7), 90 (± 7) and 180 (± 14) days post-baseline. Figure 1 shows participants' progression through the study and time points they receive the FIT intervention (if allocated to TAU + FIT) and their follow-up assessments.

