3.4.3 Participant-Reported and Clinical Outcome Measures

Outcome Measure	Baseline	28 days post-baseline	90 days post-baseline	180 days post-baseline
Alcohol use	X	X	X	X
SADQ	X	X	X	X
WEMWBS	X	X	X	X
SWEMWBS	X	X	X	X
Re-hospitalisation		X	X	X
Alcohol relapse		X	X	X
Alcohol metabolites				X
EQ-5D-5L*	X	X	X	X
Resource Use Questionnaire*	X		X	X

* please see separate HEAP

Table 1: Table detailing the timing of participant reported and other clinical outcomes

The participant-reported and clinical outcome measures listed in Table 1 will be collected in the pilot trial to help inform appropriate primary and secondary outcome measures for the definitive trial and to allow a preliminary assessment of FIT intervention in the ArLD population. The proposed primary outcome for a future definitive trial is change in self-reported alcohol use (grams of pure alcohol/week) between baseline and 180 (± 14) days post-baseline. The Timeline Follow-Back technique¹⁵ will be used to determine a participant's alcohol use during the 7 days immediately prior to: their hospital admission (baseline) and 28, 90 and 180 days post-baseline. The completeness of the Timeline Follow-Back data will also be assessed. We will report, for each visit after baseline, the number and proportion of participants who reported not taking alcohol 7 days prior to the assessment day by allocation.

Proposed secondary outcomes for a future definitive trial are the:

- *Severity of Alcohol Dependence Questionnaire (SADQ)*¹⁴ – This questionnaire consists of 20 items and covers the following areas of the dependency syndrome:
 - physical withdrawal symptoms; affective withdrawal symptoms
 - relief drinking
 - frequency of alcohol consumption
 - speed of onset of withdrawal symptoms.Each item of the questionnaire is scored between 0 (almost never) and 4 (nearly always)
- *Warwick-Edinburgh Mental Wellbeing Scale (WEMWBS)*¹⁷ – This questionnaire is a measurement of mental wellbeing, consisting of 14 items each with a score between 1 (None of the time) and 5 (all of the time)
- *Short Warwick-Edinburgh Mental Wellbeing Scale (SWEMWBS)*¹⁸ - This questionnaire is the short version of WEMWBS, consisting of 7 of the items from the full WEMWBS
- *Re-hospitalisation within 180 days post baseline* – Self-reported by participants or determined using hospital records at participating sites

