4.2 ANALYSIS POPULATIONS

Primary analysis (in the form of summary statistics such as means and standard deviations (SDs) or medians and interquartile ranges (IQR), where appropriate), will be undertaken on an Intention To Treat (ITT) basis, where participants are analysed according to their allocated group, regardless of adherence to the protocol or lack of participation or completion of FIT sessions if allocated to the intervention group. No formal (i.e. no hypothesis testing/inferential) analysis will be performed. Missing responses will be imputed according to the guidance set out in section 4.8.1. Any participants with non-imputable items/scores, will not be included in the ITT analysis for the outcome/time-point under consideration. We will present summary statistics of outcomes for participants who complete all visits in both groups. the changes between baseline and each of the 28, 90, and 180 day assessments, a participant will need to have non-missing or imputable data at both of the time points to be included in the analysis. Kaplan-Meier survivor curves will be used to characterise the time of relapse to alcohol use by group.

The safety population will include all participants who consent to participate in the study, with safety data collected from the time of recruitment until a participant completes or withdraws from the study. Any participant who does not attend at least one FIT session will be analysed as TAU and any participant who has received at least one FIT session will be analysed as TAU + FIT.

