Fibrosis			
Cirrhosis			
Child-Pugh Score			
Mean (SD) [range]			
Median (IQR)			
MELD Score			
Mean (SD) [range]			
Median (IQR)			

*Participants can provide data in more than one category – percentages will not necessarily add to 100%

Table 10: Summary statistics for the proposed primary and secondary outcome measures by allocated group

Variable	Time point	TAU			FIT + TAU		
		N	Mean (SD) (95% CI)/Median [IQR]	Range	N	Mean (SD) (95% CI) /Median [IQR]	Range
Alcohol Use (grams of pure alcohol/ week)	baseline						
	28 (±7) days						
	90 (±7) days						
	180 (±14) days						
SADQ Score	baseline						
	28 (±7) days						
	90 (±7) days						
	180 (±14) days						
WEMWBS	baseline						
	28 (±7) days						
	90 (±7) days						
	180 (±14) days						
SWEMWBS	baseline						
	28 (±7) days						
	90 (±7) days						
	180 (±14) days						
Ethyl Glucuronide (µg/L)	180 (±14) days						
Ethyl Sulphate (µg/L)	180 (±14) days						
Re- hospitalisation*	180 (±14) days						

* Rates and corresponding confidence intervals given for re-hospitalisation

Table 11: Summary statistics for the changes between baseline and 28, 90, and 180 day assessments for proposed primary and secondary outcomes including only those participants who complete all follow-up visits

Variable	Time point	TAU			FIT + TAU		
		N	Mean (SD) Change From Baseline (95% CI)/Median [IQR]	Range	N	Mean (SD) Change From Baseline (95% CI) /Median [IQR]	Range
Alcohol Use (grams of pure alcohol/ week)	28 (±7) days						
	90 (±7) days						
	180 (±14) days						
SADQ Score	28 (±7) days						
	90 (±7) days						
	180 (±14) days						
WEMWBS	28 (±7) days						
	90 (±7) days						
	180 (±14) days						
SWEMWBS	28 (±7) days						
	90 (±7) days						
	180 (±14) days						

Table 11b: Proportion of participants who completed TLFB assessment and with no alcohol consumption as calculated from TLFB

Variable	Time point	TAU	FIT + TAU
		N (% of participants with complete TLFB)	N (% of participants with complete TLFB)
Participants with zero alcohol consumption	Baseline		
	28 (±7) days		
	90 (±7) days		
	180 (±14) days		

Table 12: Re-hospitalisations by allocated group

Re-hospitalisation	TAU N (%)				FIT + TAU N (%)			
	0	1	2	>2	0	1	2	>2
No. of re-admissions								
By 28 (± 7) days								
By 90 (± 7) days								
By 180 (± 14) days								

Table 13: Proportion of participants who relapse and time to relapse to alcohol use by allocated group

	TAU	FIT + TAU
N (%) who relapsed by:		
28 (± 7) days		

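### Table 13's plain median time to relapse uses only observed relapsers, so it drops censored participants, is biased early, and will not in general agree with the planned Kaplan-Meier curves

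*SAP*

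**What the plan says.** Protocol section 4.4 proposes as a secondary outcome for the definitive trial: "Self-reported time to relapse to regular alcohol use". Relapse means at least 5 drinking days in a week or at least 5 units in one day. SAP section 3.4.3 repeats the definition, and its Table 1 gives "Alcohol relapse" its own row, marked at all three follow-ups. Those fall at "28 (± 7), 90 (± 7) and 180 (± 14) days post-baseline" (SAP section 3.1).

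On analysis, SAP section 4.2 states: "Kaplan-Meier survivor curves will be used to characterise the time of relapse to alcohol use by group". It gives no time origin, no rule for dating a relapse and no censoring rule. In SAP Appendix A, Table 13 is titled "Proportion of participants who relapse and time to relapse to alcohol use by allocated group". It has two parts: the number and percentage relapsed by each visit, and a row for time to relapse in days, to be filled with a median, interquartile range and range per group. The row does not say who is included and does not mention the Kaplan-Meier estimate.

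On data collection, the visit lists in protocol sections 10.2 to 10.4 contain one drinking item, units in the preceding week by timeline follow-back. The footnote to protocol Table 1 says: "Post-allocation, this covers the seven days prior to the data collection timepoint". SAP section 3.4.3 agrees, with follow-back covering drinking "during the 7 days immediately prior to: their hospital admission (baseline) and 28, 90 and 180 days post-baseline". No relapse question or relapse date appears in these lists or in protocol Table 1.

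**The concern.** A participant who has not relapsed when last seen has no relapse time, only a lower bound. A plain median, interquartile range and range of time to relapse therefore describe only those who relapsed while under observation. Conditioning on relapse by day 180 pulls the median early, and loss to follow-up pulls it earlier still. The same report would then carry Kaplan-Meier curves that keep the censored participants and imply a different median.

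The plain median also hides differences between groups. A group in which fewer people relapse can show nearly the same median among its relapsers.

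A second question is where the dates come from. The protocol specifies recall over the whole interval for resource use (since discharge, then since day 90), but not for drinking. If the follow-back week is the only source, relapse is known only to lie between visits, and an episode that starts and ends in a gap is never seen.

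The pilot is meant to inform the choice of outcomes for the definitive trial. A misleading summary of relapse time would give the wrong impression of this one.

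**Working it through.** **The plan's own figures.** The documents state no expected number of relapses, median relapse time or days observed. The nearest figure is the 33 per group with 180-day data: 90 × 0.75 / 2 = 33.75, rounded down to 33. It reproduces and is not affected by this point.

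**Inputs.** Visits at days 28, 90 and 180 (SAP 3.1); look-back of 7 days (protocol Table 1 footnote). The only relapse proportion in the documents is two-thirds within six months (protocol section 1), which refers to alcoholic hepatitis survivors returning to any drinking. It is used here only as one value within an assumed range of p = 50% to 80% relapsed by day 180. A constant hazard is also assumed.

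**Formulas.**
- Hazard: λ = −ln(1 − p) / 180.
- True median: ln 2 / λ.
- Plain median among those relapsed by day 180: −ln(1 − p/2) / λ.
- Proportion relapsed by day t: F(t) = 1 − exp(−λt).

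**At p = 2/3.** λ = ln 3 / 180. The true median is 180 × 0.693 / 1.099 = 113.6 days. The plain median is 180 × ln 1.5 / ln 3 = 180 × 0.405 / 1.099 = 66.4 days, which is 42% short.

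**If relapses are dated to the visit at which they are found** (assuming each is found at the next visit), F is 15.7%, 42.3% and 66.7% at days 28, 90 and 180. Among relapsers that is 23.6%, 63.4% and 100%, so the plain median is 90 days. A Kaplan-Meier curve from the same data steps only at visits, and its median reads 180.

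| Relapsed by day 180 | True median | Plain median, exact dates | Kaplan-Meier median, visit-dated | Plain median, visit-dated |
|---|---|---|---|---|
| 50% | 180 | 75 | 180 | 90 |
| 67% | 114 | 66 | 180 | 90 |
| 80% | 78 | 57 | 90 | 90 |

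The visit-dated plain median is 90 in the 50% row because F(28)/p = 0.102/0.5 = 20% and F(90)/p = 0.293/0.5 = 59%. In the 80% row the shares are 0.221/0.8 = 28% and 0.553/0.8 = 69%.

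**Contrast between groups.** With exact dates, groups at 50% and 67% relapse have true medians 66 days apart (180 and 114) but plain medians only 8 days apart (75 and 66, before rounding 74.7 and 66.4). With visit dating, all three rows give the same plain median.

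**Check with dropout.** A simulation with 45 per group, 25% uniform dropout and 5,000 runs gave, at p = 2/3, a Kaplan-Meier median of 113 days and a plain median of 61. At p = 80% the values were 77 and 52.

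**Coverage.** The follow-back weeks cover 3 × 7 = 21 of 180 days (11.7%). The gaps at nominal dates are days 1–21, 29–83 and 91–173, that is 21 + 55 + 83 = 159 days. Under a constant hazard about 11.5% of relapse onsets fall inside a window. A missed visit widens the gap, since protocol section 10.6 stops contact attempts until the next scheduled visit.

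**The case against.** The strongest reply is that the outcome is self-reported and has its own row in SAP Table 1, separate from alcohol use. A recalled date may well have been asked. The worksheets and case report form are not among the documents, and a summary visit list does not prove that an item is absent. The supplied protocol may also not be the version that the SAP cites: the SAP lists two exclusions that this protocol lacks, and one SAP table shell has four sites against the protocol's three. This stands. A reader might infer that time to relapse cannot be measured in this trial, and the documents do not support that. The 21 days limit the follow-back, not a recall question.

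Nor are non-relapsers ignored altogether, as a reader might infer from the median alone. The Kaplan-Meier curves keep them, and Table 13 gives the number relapsed by each visit. Table 13 does not say that its median is among relapsers. That is an inference, but a firm one: a range of relapse times cannot be formed for people who have none.

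The size is also open to challenge. The 66 days needs exact dates, so it cannot be combined with the complaint that relapses are dated only to visits; there the figure is 90, or 21% below 114. With visit dating at 80% relapse, the plain median (90) exceeds the true one (78) and equals the visit-dated Kaplan-Meier median. Follow-back is recorded by day (the completeness shell lists days 1 to 7), so drinking inside a window can be dated to the day.

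Finally, the trial tests no hypotheses, and relapse does not enter the progression criteria, the sample-size inputs or Tables 14 to 17. This limits the severity but does not correct the table.

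**Conclusion.** The point holds for Table 13. A plain median, interquartile range and range of relapse time exclude censored participants. With exact dates the result is early: 75 to 57 days against a true 180 to 78 for 50% to 80% relapse, and 66 against 114 at two-thirds. These sizes rest on an assumed constant hazard and assumed relapse proportions. The early direction does not depend on the hazard shape, because it follows from leaving out those who had not relapsed by the end of observation. If relapses are dated to visits, the plain median is 90 throughout that range, so it carries almost no information about the groups.

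The source of the relapse date is a separate, conditional point. If follow-back is the only source, relapse is interval-censored between visits and some episodes are missed. The documents do not settle whether dates were recalled.

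Severity is moderate: a stated summary of a descriptive secondary outcome would mislead, but no trial decision in the SAP depends on it.

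**What to change.** In SAP Table 13, replace the plain median, interquartile range and range with the following, by group:
- the Kaplan-Meier median, shown as not reached where that applies;
- Kaplan-Meier relapse probabilities at 28, 90 and 180 days with confidence intervals.

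In SAP section 4.2, state the time origin, the source of the relapse date, and that participants who have not relapsed, including those lost to follow-up, are censored at last contact. Make clear that the section's rules on non-imputable data and on completing all visits do not remove participants from this analysis.

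If no self-reported dates were collected, report the prevalence of relapse in each visit window, or an interval-censored estimate, in place of the curves.

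The cost is a few sentences and one table edit. SAP version 1.1 was written after database lock, so a new worksheet question cannot help this trial. For the definitive trial, add one item at each follow-up asking for the date on which the relapse definition was first met since the previous contact.

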16. SAFETY MONITORING

Whilst participants are unlikely to experience any harm as a direct result of taking part in this trial, processes will be implemented to ensure that such harms are detected and monitored appropriately. The safety of participants will be monitored throughout the trial, from the time that consent is obtained until the end of trial visit.

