17.5. Participant population

As described above, the primary descriptive comparative analyses of the participant-reported and other clinical outcomes will be on an intention-to-treat basis, including all the outcome data obtained from all participants, with participants analysed in the group to which they were originally allocated. Safety data (SAEs and SARs) will be presented on a per-protocol basis.

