5.1 STUDY POPULATION

Data from the screening process through to the completion of the trial will be recorded and presented in a CONSORT-style flow diagram (see Figure 2). In particular, the following data will be provided:

- Number of people invited to participate
- Number of people screened for eligibility
- Number (percentage) of people ineligible
- Number (percentage) of people eligible and asked to participate
- Number (percentage) of people who declined to participate
- Number (percentage) of people consented to participate
- Number (percentage) of participants who consented to participate but did not proceed to randomisation
- Number (percentage) of participants randomised to each allocated group
- Number (percentage) of participants who did not receive their allocated treatment
- Number (percentage) of participants who did receive their allocated treatment
- Number (percentage) of participants who completed the 28 (± 7) days post baseline assessment
- Number (percentage) of participants who completed the 90 (± 7) days post baseline assessment
- Number (percentage) of participants who completed the 180 (± 14) days post baseline assessment
- Number (percentage) of participants lost to follow up
- Number (percentage) of participants analysed

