5.4 SAFETY DATA

The likelihood of participants being harmed by either the FIT intervention or any of the trial procedures is very low. As such, the reporting of adverse events in the MIRAGE trial is restricted to only those events that are serious, which

- results in death
- Is life-threatening
- Requires inpatient hospitalisation or prolongation of existing hospitalisation
- Results in a persistent or significant disability/incapacity
- Is a significant or important medical event

All serious adverse events reported after the participant has consented to take part in the trial will be reported by treatment group, whereby any participant who has received at least one FIT session will be included in the TAU + FIT treatment group.

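### Grouping SAEs by FIT attendance, among everyone who consents, breaks the randomised safety comparison; the direction of the resulting bias is unknown

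*SAP*

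**What the plan says.** SAP 4.2 defines the population: "The safety population will include all participants who consent to participate in the study". It then assigns groups by what was received. On one side, "Any participant who does not attend at least one FIT session will be analysed as TAU"; on the other, "any participant who has received at least one FIT session will be analysed as TAU + FIT". SAP 5.4 repeats the second half for SAE reporting: "whereby any participant who has received at least one FIT session will be included in the TAU + FIT treatment group".

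Protocol 17.5 uses a different term: "Safety data (SAEs and SARs) will be presented on a per-protocol basis". It does not define it.

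Three other places matter for how the rule works:

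- Protocol 16 monitors safety "from the time that consent is obtained until the end of trial visit".
- Protocol 10.5.1 lets FIT session 1 fall anywhere between randomisation and discharge.
- SAP 5.1 expects patients who consent and go no further, since the flow diagram reports "Number (percentage) of participants who consented to participate but did not proceed to randomisation".

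For clinical outcomes the same SAP section keeps participants in their allocated group whether or not they attend FIT.

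**The concern.** The SAE clock starts at consent, but the group label depends on a later event. If a FIT-allocated patient dies, deteriorates or loses capacity before session 1, both the patient and the event are counted under TAU. Prolongation of the index stay is itself an SAE (Protocol 16.1), and a participant who loses capacity is withdrawn because FIT cannot be given (Protocol 9.3). The event that blocks FIT can therefore also be the one that changes columns. Control patients are not offered FIT, so the expected movement is from FIT to TAU only.

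A consented but unrandomised patient has attended no FIT session and so meets the rule for TAU, although that patient belongs to no arm.

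At stake is whether the SAE columns can be read as a comparison of randomised groups. SAEs here include every unplanned admission and ED visit (Protocol 16.1), so counts may not be small and readers will compare the columns.

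**Working it through.** **The plan's own figures.** Protocol 17.1: 150 x 0.60 = 90, so 45 per arm at 1:1. At 75% retention, 45 x 0.75 = 33.75, which agrees with the stated minimum of 33. The 95% half-width at n = 90 and p = 0.5 is 1.96 x sqrt(0.25/90) = 10.3 points, within the stated 11. None of these figures concerns safety, and no SAE rate, non-starter rate or number unrandomised is given.

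**Inputs.**

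- Arm size 45, from the documents.
- m = would-be non-starters in each arm (assumed 5, 9 or 13). SAP Table 2 rates FIT adherence green above 70%. With 13 of 45 failing, adherence is 32/45 = 71%, so 13 is the most non-starters that green allows.
- ps = SAE risk in starters (assumed 40%).
- pn = SAE risk in non-starters (assumed 20% to 80%).
- u = unrandomised consenters, with recorded SAE risk pu (assumed).

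**Formula, no true FIT effect, u = 0.**

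- FIT column: only starters remain, so the risk is ps.
- TAU column: [(45 - m) x ps + 2m x pn] / (45 + m).
- FIT minus TAU = -(pn - ps) x 2m / (45 + m).

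For m = 9 and pn = 80%: TAU = (36 x 0.4 + 18 x 0.8)/54 = 28.8/54 = 53.3%. FIT = 40%, so the difference is -13.3 points.

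| m | pn = 80% | pn = 60% | pn = 40% | pn = 20% |
|---|---|---|---|---|
| 5 | -8 | -4 | 0 | +4 |
| 9 | -13 | -7 | 0 | +7 |
| 13 | -18 | -9 | 0 | +9 |

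Entries are FIT minus TAU in percentage points; negative makes FIT look safer. Grouped by allocation among randomised patients, every cell is 0.

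**Adding unrandomised patients** (m = 0, both arms at 40%, u = 10). TAU = (18 + 10 x pu)/55.

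- pu = 0%: 18/55 = 32.7%, so FIT looks 7 points worse.
- pu = 10%: 19/55 = 34.5%, so FIT looks 5 points worse.
- pu = 80%: 26/55 = 47.3%, so FIT looks 7 points better.

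With m = 5 at 80% and u = 10 at 0%, TAU = 24/60 = 40% and the two effects cancel.

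**Could a real harm be hidden?** Suppose FIT adds 10 points in starters (50% v 40%), with m = 9 and pn = 80%.

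- By allocation: FIT = (36 x 0.5 + 9 x 0.8)/45 = 56%; TAU = (14.4 + 7.2)/45 = 48%; difference +8 points.
- As received: 50% v 53.3%, a difference of -3 points.

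**The case against.** Reporting safety by exposure is a recognised convention: a patient who attended no FIT session cannot have had a reaction to FIT. That stands, and it is a reason to keep the as-received table. It is not a reason to have no table by allocation, or to give unrandomised patients an arm.

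A reader might infer that the rule makes FIT look safer. The documents do not support this. It needs non-starters to have more recorded SAEs than starters, and there are reasons why they may not:

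- SAEs are found mainly at research contacts (Protocol 16.3), and failed calls are not pursued until the next scheduled visit (Protocol 10.6), so disengaged patients may have fewer on record.
- Patients withdrawn for loss of capacity have no further research visits (Protocol 9.3), and SAP 4.2 ends safety collection at withdrawal.
- Events between consent and session 1 in patients who later attend are counted under FIT, which runs against FIT.
- Unrandomised patients with short observation would usually lower the TAU rate.

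A reader might also take the protocol's per-protocol wording as a further population that drops non-adherers. The term is undefined and may be loose wording for as-received. What can be shown is that the two documents name different rules.

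The consequence is limited. No between-group tests are planned (SAP 4.3), and safety is not a progression criterion (SAP 5.5). Causality is judged event by event (Protocol 16.4 and 16.5), and the TSC sees quarterly line listings (Protocol 16.9). SAP Table 12 already gives re-hospitalisation by allocated group. These safeguards are real but partial: Table 12 does not cover deaths, prolonged index stays or ED-only visits, and the first two are among the events most likely to prevent session 1.

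**Conclusion.** The defect in the rule is established from the text. SAP 4.2 and 5.4 group SAEs by an event after randomisation, in a population that includes people who were never randomised, and no passage provides SAEs by allocation. The randomised SAE comparison is lost, and the SAP and Protocol 17.5 do not agree.

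Neither direction nor size is established. Across the non-starter scenarios in the table the spurious difference runs from -18 to +9 points, and it is 0 when non-starters and starters carry equal recorded risk. These figures rest on assumed SAE risks and assumed numbers of non-starters, and are illustrations only. A conclusion that the plan is tilted in favour of FIT would go beyond the documents. The supportable conclusion is that the planned SAE contrast has a possible bias of unknown sign and so cannot be interpreted as a treatment comparison.

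This should be fixed, but in a descriptive pilot no planned decision rests on it.

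**What to change.** - In SAP 4.2 and 5.4, report SAEs by allocated group for all randomised participants.
- List events before randomisation, and events in patients never randomised, separately and without an arm.
- Keep the as-received grouping as a supplementary table, labelled as such.
- Reword Protocol 17.5 so that it names the same presentations as the SAP.

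The cost is one additional table, a short listing and wording changes in two documents. No new data are needed: allocation, FIT attendance and event dates are already collected.
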